## **5.4. Secondary Endpoints Analysis**

### **5.4.1. Secondary Immunogenicity Endpoints**

#### **5.4.1.1. Definition of Endpoints**

The secondary immunogenicity endpoints are:

- If a participant has positive N serology, then the individual is considered seropositive.

When including vaccine naive individuals in the analysis, if the individual has detectable S Elisa titers above the limit of quantification and/or positive N serology, then the individual is considered seropositive. The confirmation of serostatus will be performed with a sensitive S-ELISA and/or N serology assay.

- Previous history of vaccination defined as previously vaccinated individuals (ie, Vaxzevria [AstraZeneca], Comirnaty [Pfizer-BioNTech], SpikeVax [Moderna], and Ad26.COV2-S [Janssen]), regardless of previous SARS-CoV2 infection.

The following will be presented descriptively for the secondary analyses:

- Humoral immune response as measured by the HI assay after concomitant administration of Ad26.COV2.S vaccine and a seasonal quadrivalent *standard-dose* influenza vaccine versus the administration of a seasonal quadrivalent *standard-dose* influenza vaccine alone, 28 days after the administration of a seasonal influenza vaccine.
- Humoral immune response (ELISA) following concomitant administration of Ad26.COV2.S vaccine and a seasonal quadrivalent *standard-dose* influenza vaccine versus the administration of Ad26.COV2.S vaccine alone, 28 days after the administration of Ad26.COV2.S vaccine.
- Humoral immune response as measured by the HI assay after concomitant administration of Ad26.COV2.S vaccine and a seasonal quadrivalent *high-dose* influenza vaccine versus the administration of a seasonal quadrivalent *high-dose* influenza vaccine alone, 28 days after the administration of a seasonal influenza vaccine.
- Humoral immune response (ELISA) following concomitant administration of Ad26.COV2.S vaccine and a seasonal quadrivalent *high-dose* influenza vaccine

versus the administration of Ad26.COV2.S vaccine alone, 28 days after the administration of Ad26.COV2.S vaccine.

For COVID-19 vaccine-naïve individuals, the following will be presented:

- Humoral immune response (ELISA) following concomitant administration of Ad26.COV2.S vaccine and a seasonal quadrivalent *high-dose* influenza vaccine versus the administration of Ad26.COV2.S vaccine alone, 28 days after the administration of Ad26.COV2.S vaccine in COVID-19 vaccine-naïve individuals.
- Humoral immune response (ELISA) following concomitant administration of Ad26.COV2.S vaccine and a seasonal quadrivalent *standard-dose* influenza vaccine versus the administration of Ad26.COV2.S vaccine alone, 28 days after the administration of Ad26.COV2.S vaccine in COVID-19 vaccine-naïve individuals.

The HAI analysis is based on vaccine specific strains, therefore, for the *high dose* of the flu vaccine (descriptive analysis) the following vaccine-specific strains will be used:

A/Victoria (H1N1)  
A/Tasmania (H3N2)  
B/Washington (B/Victoria)  
B/Phuket (B/Yamagata)

#### **5.4.1.2. Analysis Methods**

To assess the humoral immune response to SARS-CoV-2 in vaccination groups, the following statistics will be calculated for the different assays for each vaccination group at each time point: N, geometric mean and corresponding 95% CI of the actual values, fold increase from baseline, number of positive samples, the number of responders (see Section 5.3.2).

To compare seroconversion and seroprotection rates against the 4 influenza vaccine strains, the proportion of seroconverted and seroprotected participants will be tabulated. The difference in proportions of seroconverted and seroprotected participants between the Control and the CoAd group will be estimated together with the 2-sided 95% CIs (calculated using Wilson's score method).

Additionally, HI antibody titers and S-ELISA titers will be summarized with descriptive statistics. Descriptive statistics (geometric mean and 97.5% CI) of the actual values will be calculated for continuous immunogenicity parameters at all timepoints. Geometric mean fold increases from baseline and corresponding 95% CIs might additionally be calculated. Graphical representations of immunogenicity parameters will be created as applicable.

For categorical variables, frequency tables will be presented. Difference in proportions and corresponding CIs may be calculated where appropriate.

Actual values and fold changes from baseline will also be presented in dot-plots with dots for participant values, and the corresponding geometric mean and 95% CI per timepoint for each assay. In addition, plots of GMT over time, combining the regimens in one graph (without individual participant dots) will be created. Participant profiles of the actual values over time will be graphically presented. Reverse distribution curves of the actual values will be provided for selected timepoints. In the graphs, original values will be displayed on the  $\log_2$  or  $\log_{10}$  scale.

Refer to Section 5.3.3 for instructions on how immune response values below LLOQ, values above ULOQ / Max Range and missing values will be handled.

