9.2. Sample Size Determination

Sample size calculations are performed under the following assumptions:

- no effect of co-administration of Ad26.COV2.S vaccine and seasonal influenza vaccine on the immune response against influenza as measured by HI antibody titers against the 4 influenza vaccine strains at 28 days after the administration of seasonal influenza vaccine
- the use of Afluria Quadrivalent for *standard-dose* (adults ≥ 18 to < 64 years of age and older adults ≥ 65 years of age)
- a standard deviation of 0.53 for the *standard-dose* at the \log_{10} scale for HI antibody titers against the 4 influenza vaccine strains at 28 days after the administration of seasonal influenza vaccine (with or without Ad26.COV2.S)
- no effect of co-administration of Ad26.COV2.S vaccine and seasonal influenza vaccine on the immune response against SARS-CoV-2 as measured by S-ELISA at 28 days after the administration of Ad26.COV2.S vaccine
- a standard deviation of 0.50 at the \log_{10} scale for S-ELISA at 28 days after the administration of Ad26.COV2.S vaccine (with or without seasonal influenza vaccine)
- a NI margin of 1.5
- 2-sided α of 5%

A total of approximately 305 (*standard-dose*) participants per group (total N 610) who have completed a primary COVID-19 vaccine series are needed to have 97.45% power to show NI in HI antibody titers for 1 influenza vaccine strain.

The sample size accounts for exclusions from the per protocol set (see Section 9.3), drop-outs and missing samples.

With this sample size, the overall power to show NI in HI antibody titers against each of the 4 influenza vaccine strains at 28 days after the administration of seasonal influenza vaccine as well as NI in S-ELISA at 28 days after the administration of Ad26.COV2.S vaccine is at least 90%.

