## **5.7. Other Analyses**

### **5.7.1. Subgroup Analysis**

For exploratory purpose, subgroup analyses for the primary endpoints (and vaccine-naïve participants) related to humoral response will be done (but are not limited) for the following subgroups if significant balance is achieved:

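### The high-dose and vaccine-naïve secondary objectives compare co-administration with separate administration, but no Control/CoAd GMT or GMC ratio with a confidence interval is planned for them

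*SAP*

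**What the plan says.** The objectives tables (Protocol 3, SAP 1.1) set HI GMT and S-ELISA GMC in the high-dose groups, and S-ELISA GMC in vaccine-naïve participants at each influenza dose, as co-administration against a separately given vaccine. SAP 5.4.1.1 fixes the level of analysis: "The following will be presented descriptively for the secondary analyses". Protocol 9.4.3 says the same, and Protocol 9.1 rules out formal testing in the high-dose groups.

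SAP 5.4.1.2 then gives the statistics. For the SARS-CoV-2 response they are, for each vaccination group, "N, geometric mean and corresponding 95% CI of the actual values, fold increase from baseline, number of positive samples, the number of responders". For HI and S-ELISA together it adds geometric means with an interval, optional fold increases, and plots. It also plans a Control versus CoAd difference, with a 2-sided 95% interval by Wilson's score method, for seroconversion and seroprotection. Those two endpoints cover both influenza doses.

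The back-transformed ratio with its interval appears in SAP 5.3.2. It is written for the non-inferiority objectives, which SAP 5.3.1 ties to the standard-dose groups.

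**The concern.** An objective phrased as one regimen against another calls for an estimate of the contrast. For these GMT and GMC endpoints the plan describes each group separately and stops there. Dropping the formal test in the high-dose groups removed the hypothesis, not the comparison.

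The stakes are modest but real. If the ratio and its covariates are not fixed before unblinding, any ratio reported later is post hoc, with the model chosen after the data are seen. The readers most affected are those asking about the high-dose vaccine in people aged 65 or older and about vaccine-naïve recipients, for whom these secondary results are the trial's answer.

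**Working it through.** **1. Which comparative endpoints have a between-group estimate?**

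| Secondary endpoint | Per-group summary | Between-group estimate with interval |
|---|---|---|
| HI seroconversion, seroprotection (both doses) | yes | yes, difference in proportions (SAP 5.4.1.2) |
| HI GMT, high-dose | yes | none specified |
| S-ELISA GMC, high-dose | yes | none specified |
| S-ELISA GMC, vaccine-naïve, each dose | yes | none specified |

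SAP 5.4.1.2 also allows, where appropriate, a difference in proportions for categorical variables. That could reach the S-ELISA responder rate, but not the GMC.

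**2. Inputs (Protocol 9.2).** "2-sided α of 5" percent; "a NI margin of 1.5"; "a standard deviation of 0.53 for the" standard-dose HI titers on the log10 scale; "a standard deviation of 0.50 at the" log10 scale for S-ELISA; 305 "participants per group (total N 610) who have completed a primary COVID-19 vaccine series". SAP 3 adds a loss allowance of about 10%, or about 30 per group.

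**3. The plan's own figure reproduces.** Margin = log10(1.5) = 0.1761. Power = Φ(0.1761 / (0.53 × √(2/n)) − 1.96). With n = 305 − 30 = 275: 0.53 × √(2/275) = 0.0452; 0.1761/0.0452 − 1.96 = 1.936; power 97.36%. At n = 278 it is 97.48%. The stated 97.45% therefore corresponds to about 278 evaluable per group. This calculation covers previously vaccinated standard-dose participants only. No size is stated for the high-dose or vaccine-naïve groups.

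**4. Precision of the missing ratio.** For an unadjusted two-group ratio, the 95% interval is the estimate multiplied and divided by 10^(1.96 × SD × √(2/n)). Two assumptions are needed: n, which is not given, and the SD. The 0.53 is stated for standard-dose HI only, and no separate S-ELISA SD is given for vaccine-naïve participants.

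| n per group | HI, SD 0.53 | S-ELISA, SD 0.50 |
|---|---|---|
| 25 | 1.97 | 1.89 |
| 50 | 1.61 | 1.57 |
| 100 | 1.40 | 1.38 |
| 150 | 1.32 | 1.30 |
| 200 | 1.27 | 1.25 |
| 245 | 1.24 | 1.23 |

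Example, S-ELISA at n = 50: 1.96 × 0.50 × √(2/50) = 0.196, and 10^0.196 = 1.57.

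The last row is a ceiling for the high-dose groups. If the approximate totals of 1,100 and 610 are both met, 1,100 − 610 = 490 remain for the high-dose groups and the vaccine-naïve standard-dose participants together, so each high-dose group has at most 490/2 = 245 before losses.

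**5. Which covariates can enter.** Groups 3 and 4 are all aged 65 or older, so age category is constant there, while prior COVID-19 vaccination varies. Among vaccine-naïve participants prior vaccination is constant, and age category varies only in the standard-dose or pooled comparison. SAP 5.4.1.1 defines serostatus for analyses that include vaccine-naïve people partly from quantifiable S-ELISA, so serostatus and baseline S-ELISA titer overlap.

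**The case against.** The strongest reply is that this is a disclosed choice. Amendment 1 replaces the high-dose non-inferiority assessment with a descriptive one, and the objectives say assess, not demonstrate. It stands in part: no test, margin or non-inferiority claim is owed. But a description can include an estimated contrast, and SAP 5.4.1.2 already gives one, with an interval and no test, for the two HI proportions.

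A reader could also work out an unadjusted ratio and interval from each group's N, geometric mean and t-based log-scale interval. That is true. An adjusted ratio cannot be recovered this way, and nothing would be prespecified.

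Other routes exist but are weak. SAP 5.5.2 says that analyses by vaccination history, vaccine-naïve included, use methods similar to 5.3.2 and 5.4.1.2; it is exploratory and names no contrast. SAP 1 refers to a Data Presentation Specification that is not among the documents and might add outputs, but the estimator for a secondary objective belongs in the SAP.

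Four stronger readings are tempting and not supported:
- A reader might infer that the plan has no between-group interval at all. The seroconversion and seroprotection differences show otherwise, and the per-group summaries include fold increase and responders.
- A reader might infer that results will be judged by whether two intervals overlap. Nothing in the plan proposes that.
- A reader might infer that prior infection is examined in vaccine-naïve participants only if the condition in SAP 5.7.1 is met, where subgroup analyses "will be done (but are not limited) for the following subgroups if significant balance is achieved". SAP 5.5.1 lists response by baseline N-serology as an exploratory endpoint without that condition. Nor can the effect of an infection imbalance, or the gain from adjusting for it, be sized: the documents give neither the share infected nor the effect of infection on titer.
- A reader might infer that the high-dose ratio would be decisive against 1.5. That margin belongs to the standard-dose objectives, and the high-dose sizes are unstated. Even at an assumed 100 per group, the S-ELISA upper limit falls below 1.5 only if the estimate is under 1.5/1.376 = 1.09.

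**Conclusion.** The point holds for the high-dose HI GMT, high-dose S-ELISA GMC and vaccine-naïve S-ELISA GMC objectives, and no further. Each is comparative; none has a specified Control/CoAd ratio with an interval. The primary analysis and its power are unaffected.

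The size of the gap is the absence of the estimate, not a known bias. What the estimate would deliver depends on unstated group sizes: at SD 0.50 the interval factor runs from about 1.89 at 25 per group to 1.25 at 200. These figures assume equal groups, the planning SDs carried over to the high-dose and vaccine-naïve groups, and no covariate adjustment.

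**What to change.** In SAP 5.4.1.2, for Group 3 versus Group 4 and for vaccine-naïve participants (in the PPSI2 set, by dose, or pooled with a dose term if sparse), add the Control/CoAd GMT or GMC ratio with a nominal 2-sided 95% interval, labelled as carrying no non-inferiority claim.

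Estimate it from a log-titer model with group and the same assay's pre-vaccination titer. Add prior COVID-19 vaccination only where it varies (Groups 3 and 4) and age category only where it varies (vaccine-naïve standard-dose or pooled). In vaccine-naïve participants choose in advance either baseline S-ELISA titer or Day 1 serostatus; both are not necessarily needed.

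Two inconsistencies should be settled in the same edit. SAP 5.4.1.2 gives both 95% and 97.5% intervals for geometric means. SAP 1.1 names influenza vaccine alone as the comparator for the high-dose S-ELISA objective, whereas SAP 5.4.1.1 and Protocol 3 name Ad26.COV2.S alone.

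The cost is SAP wording and a few more model outputs, with no new data or participants. The downside is that small vaccine-naïve cells may force strata to be collapsed.

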#### **5.4.2. Secondary Safety Endpoints**

See Section 5.6.

### **5.5. Exploratory Endpoints Analysis**

#### **5.5.1. Definition of Endpoints**

The exploratory endpoints are:

- GMT: Geometric mean of HI antibodies and percentages of participants with HI titers  $\geq 1:40$ , *at Day 181*.
- Antibody GMC by S-ELISA *at Day 181* after the administration of Ad26.COV2.S vaccine.
- Serological responses *magnitude and durability at Day 181* to vaccination as measured by ELISA at Day 181 after the administration of influenza vaccine.
- Serological response to vaccination, as measured by virus neutralization assay (VNA) (SARS-CoV-2 VNA and/or pseudo virion [ps] VNA expressing S protein) titers, in a subset of participants.
- Adenovirus 26 neutralization responses measured by VNA.
- Functional and molecular antibody characterization including Fc-mediated viral clearance, avidity, Fc characteristics, immunoglobulin (Ig) subclass, and IgG isotype.
- Humoral responses to Ad26.COV2.S and influenza vaccine based on the SARS-CoV-2 serostatus at baseline (N-serology).
  - Serological response to vaccination as measured by S-ELISA antibody concentration 28 days after the administration of Ad26.COV2.S vaccine
  - Antibody GMC by S-ELISA at 28 days after the administration of Ad26.COV2.S vaccine.
  - Antibody HI titers as measured by HAI assay titers (GMTs) against the 4 influenza strains.
- Humoral responses to Ad26.COV2.S and influenza vaccine based on the previous history of COVID-19 vaccination at entry (viral vector vaccine or mRNA vaccine or vaccine-naïve)
  - Serological response to vaccination as measured by S-ELISA antibody concentration 28 days after the administration of Ad26.COV2.S vaccine.
  - Antibody GMC by S-ELISA at 28 days after the administration of Ad26.COV2.S vaccine.

- Antibody HI titers as measured by HAI assay titers (GMTs) against the 4 influenza strains.

### **5.5.2. Analysis Methods**

For humoral or serological response to vaccination method, *at Days 1, 29, 57 and 181*, and for *durability at Week 28 or as measured by virus neutralization assay (VNA)*, or *based on history of vaccination at entry* (it could be: Vaxzevria [AstraZeneca], Comirnaty [Pfizer-BioNTech], SpikeVax [Moderna], and Ad26.COV2-S [Janssen] or naïve), the methods are similar to those used for humoral immune response for primary and secondary endpoints (see Section 5.3.2 and 5.4.1.2).

Adenovirus 26 neutralization will be measured in all subjects at baseline to assess the seroprevalence of Ad26 and to assess immunogenicity against the vector. Descriptive statistics (N, geometric mean and corresponding 95% CI, number and percentage of positive samples) will be calculated.

In case there is a significant number of seropositive participants, Spearman correlation between Ad26 neutralizing antibody concentrations and S-ELISA concentrations in the combined regimens will be calculated and will be visualized with a scatter plot.

SARS-CoV-2 neutralizing titers in serum measured by VNA i.e. (wild-type virus and/or pseudovirion[ps] expressing S protein) at all selected timepoints i.e. Day 1 (pre-vaccination) i.e. Baseline, Day 29, Day 57 and Week 24 (and in case of early exit at the exit visit), for a subset of the participants.

The correlation between the binding antibody (S-ELISA) concentrations and neutralizing antibody (VNA) titers to SARS-CoV-2 will be assessed at the different timepoints in a subset of participants using Spearman's rank correlation. A scatterplot between S-ELISA and VNA will be provided at the different time points.

### **5.6. Safety Analyses**

The Safety and reactogenicity endpoints (secondary endpoints) are:

- Solicited local (injection site) and systemic AEs for 7 days after each vaccination
- Unsolicited AEs for 28 days after each vaccination
- SAEs, MAAEs, and AESIs throughout the study.
- AEs leading to withdrawal from the study throughout the study.

These endpoints will be assessed in both participants aged *65 years and older*, and participants aged *18 years and older*.

## **5.6.1. Adverse Events**

### **5.6.1.1. Definitions of Adverse Events Endpoints**

Solicited AEs shown in the tables are extracted from the investigator assessment pages (CE) of the CRF. For unsolicited AEs, only the AEs within the 28-day period following each vaccination will be presented in the safety tables except for SAE, MAAEs and AESI cases which will be captured and tabulated in the outputs covering the whole study period.

Local solicited AEs symptoms will be by definition considered as related to the study vaccine.

The severity of the AEs will be classified as toxicity grade 1 to 4 (refer to appendix 7). Solicited events of grade 0, not reported in the CE domain, will therefore not be reported in the AE analysis.

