All unsolicited AEs and special reporting situations, whether serious or non-serious, will be reported for each vaccination from the time of vaccination until 28 days post-vaccination. Unsolicited adverse events with the onset date outside the timeframe defined above (>28 days after each study vaccination), which are ongoing on the day of the subsequent vaccination, should be recorded as such.

At each visit the participant will be asked if they have had a private/off-study COVID-19 test. If a participant receives a positive SARS-CoV-2 result from a private/off-study test during the study period (whether through PCR or serological testing) the event should be reported as an AE or as an SAE if the event meets the criteria of an SAE. The participant can continue in the study in accordance with local country and site level recommendations for COVID-19. Any positive SARS-CoV-2 result should be recorded in the eCRF. Previous SARS-CoV-2 infection should be documented as medical history and does not preclude participation in the study.

All SAEs, AESIs, and AEs leading to discontinuation from the study/vaccination (regardless of the causal relationship) are to be reported from the moment of first vaccination until the end of the study, which may include contact for safety follow-up. The sponsor will evaluate any safety information that is spontaneously reported by an investigator beyond the time frame specified in the protocol.

MAAEs are defined as AEs with medically-attended visits including hospital, emergency room, urgent care clinic, or other visits to or from medical personnel for any reason. Routine medical visits for chronic comorbidities (or study visits) will not be considered medically-attended visits. New onset of chronic diseases will be collected as part of the MAAEs. MAAEs are to be reported for all participants throughout the study.

As long as the participant remains in the study, all AEs will be followed until resolved, until clinically stable or the end of the study, as applicable. The investigator's assessment of ongoing AEs at the time of each participant's last visit should be documented in the participant's medical chart.

Adverse Events of Special Interest

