9.4.5. Safety Analyses

No formal statistical testing of safety data is planned. All safety data will be analyzed descriptively by group. All safety analyses will be based on the FAS.

Adverse Events

The verbatim terms used in the eCRF by investigators to identify AEs will be coded using the Medical Dictionary for Regulatory Activities (MedDRA). All reported AEs with onset during the active vaccination phase (ie, AEs occurring after vaccination up to 28 days post-vaccination), and all SAEs/MAAEs/AESIs will be included in the analysis. (S)AEs caused by molecularly confirmed SARS-CoV-2 infection will be removed at the analysis level from the (S)AE listings and tables and presented separately. For each AE, the percentage of participants who experience at least 1 occurrence of the given event will be summarized by vaccine group.

Summaries, listings, datasets, or participant narratives may be provided, as appropriate, for those participants who die, who discontinue study vaccine due to an AE, or who experience a severe AE, an AESI, or an SAE.

Solicited local (at injection site) and systemic AEs will be summarized descriptively. The number and percentages of participants with at least one solicited local (at injection site) or systemic AE will be presented. The frequencies by vaccine group as well as frequencies according to severity and duration will be described for solicited AEs. Frequencies of unsolicited AEs, separately for all and vaccination-related only, will be presented by System Organ Class and preferred term, while those of solicited AEs will be presented only by preferred term.

Clinical Laboratory Tests

Laboratory data (abnormal or graded, when available) will be listed and/or tabulated by participant and time point.

Vital Signs

Vital signs including temperature, pulse/heart rate, respiratory rate, and blood pressure (systolic and diastolic) will be summarized over time, using descriptive statistics and/or graphically. The percentage of participants with values beyond clinically important limits will be summarized.

Physical Examinations

Physical examination findings will be summarized at baseline. Physical examination abnormal findings will be listed.

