### **5.6.1.2. Analysis of Adverse Events**

Safety analyses will be performed on the FAS. Continuous variables will be summarized using the following statistics, as appropriate: number of observations, median, minimum, and maximum. Frequencies and percentages (one decimal place) will be generated for categorical variables. No formal comparisons between groups will be provided.

Safety data will be analyzed and presented by study intervention and phase. Denominator for the percentages is the number of participants in the considered population and phase for a certain regimen (incidence per 100 participants/phase).

Number and percentage of participants with at least one particular AE (unsolicited/solicited) will be tabulated. Unsolicited AEs will be summarized by System Organ Class and Preferred Term. Solicited AEs will be summarized by class (administration site, systemic) and preferred term.

For solicited AEs, the following tables will be provided: summary, by worst severity grade, at least grade 3, related (systemic only), time to onset (in days) and duration (in days). Note: Duration is defined as number of days from the start of the event until resolution of the event. The time to first onset is defined as (date of first onset – reference date + 1). The reference date is the start date of the vaccination period.

A tabulation of the distribution of temperatures per half degree intervals will also be provided.

For unsolicited AEs, the following tables will be provided: summary table (including SAE, fatal outcome, discontinuation and AESI), all events, most frequent, at least grade 3, permanent stop of vaccine, related, SAE, related SAE, potential AESI and AESI.

Unsolicited non-serious adverse events collected outside the 28-day period following the vaccination will be presented through listings.

Listings and/or participant narratives will be provided as appropriate, for those participants with a fatal outcome, discontinue study vaccinations due to an AE, discontinue study due to an AE, or experienced a severe SAE, or an AESI event.

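### SAP 5.6.1.1 omits AEs leading to study withdrawal from its whole-study table exceptions, so late withdrawal AEs that are not SAEs, MAAEs or AESIs are listed but not counted by group

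*SAP*

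**What the plan says.** The objectives tables in both documents and SAP 5.6 set out four safety endpoints. Two of them run for the whole study: SAEs, MAAEs and AESIs as one, and, as a separate item, "AEs leading to withdrawal from the study throughout the study".

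Collection matches the endpoint. The Schedule of Activities (Protocol 1.3.1) marks these events for recording for the whole study, and Protocol 8.3.1 says that "AEs leading to discontinuation from the study/vaccination (regardless of the causal relationship) are to be reported from the moment of first vaccination" to the end of the study.

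The table rules do not match it:

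- SAP 5.6.1.1 restricts the tables of unsolicited events as follows: "only the AEs within the 28-day period following each vaccination will be presented in the safety tables except for SAE, MAAEs and AESI cases". The three excepted categories are those "which will be captured and tabulated in the outputs covering the whole study period".
- SAP 5.6.1.2 adds: "Unsolicited non-serious adverse events collected outside the 28-day period following the vaccination will be presented through listings".
- The unsolicited AE tables named in SAP 5.6.1.2 begin with "summary table (including SAE, fatal outcome, discontinuation and AESI), all events, most frequent, at least grade 3, permanent stop of vaccine". The discontinuation entry is given no period.
- SAP 5.6.1.2 promises listings and/or narratives, as appropriate, for participants who "discontinue study vaccinations due to an AE, discontinue study due to an AE, or experienced a severe SAE, or an AESI event", among others.
- Protocol 9.4.5 has the same gap. It takes AEs from the 28 days after vaccination "and all SAEs/MAAEs/AESIs will be included in the analysis", and does not name withdrawal AEs.

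**The concern.** One of the two whole-study safety endpoints was carried into the exception and the other was not. A programmer who follows SAP 5.6.1.1 literally would leave some events that belong to a named secondary endpoint out of its table, although the data are in the database. A listing or narrative shows that an event happened, but it gives no number and percentage by vaccine group, which is the form in which the SAP reports every other safety endpoint. What is at stake is whether a pre-specified descriptive safety endpoint is reported as defined. The non-inferiority conclusions are not touched.

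**Working it through.** **1. Check the follow-up period against the plan's own figure.** Inputs from Protocol 1.3.1: screening up to 28 days before Day 1; vaccinations on Day 1 and Day 29, so 28 days apart; last visit 180 days after vaccination 2.

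- With full screening: 28 + 28 + 180 = 236 days; 236 / 30.4375 = 7.75 months.
- With same-day screening: 28 + 180 = 208 days; 208 / 30.4375 = 6.8 months.

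This agrees with the stated duration of approximately 7-8 months.

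**2. Share of follow-up inside the table windows.** From first vaccination to last visit is 208 days. The windows cover 28 + 28 = 56 days.

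- Inside: 56 / 208 = 26.9%.
- Outside: 208 - 56 = 152 days; 152 / 208 = 73.1%.

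Under other readings of the schedule, the share inside is:

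- vaccination 2 and last visit each 7 days late: 56 / (28 + 7 + 187) = 56 / 222 = 25.2%;
- vaccination 2 three days early and last visit 7 days early: (25 + 28) / (25 + 173) = 53 / 198 = 26.8%;
- Week 28 label taken literally as 196 days: 56 / 196 = 28.6%;
- 7 to 8 months taken as the denominator (213 to 243.5 days, which includes screening): 26.3% to 23.0%.

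The range is therefore about 23% to 29%.

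**3. Trace withdrawal AEs through the rules.** On the nominal schedule the second window ends at Day 57. SAP 5.6.1.3 allocates an AE by its start date.

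- Onset Day 40, withdrawal on Day 90: onset is inside a window, so the event is in the tables.
- Onset Day 80, serious or an AESI: excepted, so tabulated for the whole study under that heading.
- Onset Day 80, non-serious, with a medical visit: an MAAE, so excepted by 5.6.1.1. The list of tables in 5.6.1.2 names no MAAE table, and its listings-only rule for late non-serious AEs does not exempt MAAEs, so this route is less clean than the other two. I take 5.6.1.1 as governing.
- Onset Day 80, non-serious, no medical visit, not an AESI: listings or narrative only, and missing from the by-group count.

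The strict gap is the last case. In the second and third cases the event is tabulated, but as an SAE, AESI or MAAE; no table counts whole-study withdrawals due to AEs as such.

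**4. Look for something that restores the endpoint.**

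- The discontinuation entry in the summary table has no stated period, so the general 28-day rule can be read as applying to it.
- The table for permanent stop of vaccine concerns a different event. The last vaccination is on Day 29, so it cannot capture withdrawals during follow-up.
- The disposition summary in SAP 5.2 is discussed under the objection.

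**5. Effect of the change.** Adding withdrawal AEs to the exceptions raises coverage from 56 of 208 days to 208 of 208. The documents give no expected number of such events, so the count lost cannot be computed.

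**The case against.** The case for leaving the text alone has several parts.

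*The endpoint may already be covered.* The discontinuation row stands beside SAE and AESI, both whole-study categories, and SAP 5.6 gives the endpoint its own whole-study period, so a programmer might well apply that period. SAP 5.2 also summarizes, by group and throughout the study, participants who discontinued and the reasons for termination. Output details are left to a Data Presentation Specification that is not among the documents. This makes the outcome uncertain but does not settle it. The row has no stated period, while 5.6.1.1 says that only events in the window enter the tables. The disposition summary is not an AE table, and Protocol 7.2 names loss to follow-up, withdrawn consent, death and repeated non-compliance as withdrawal reasons, not an adverse event. The specification may resolve the matter, but it cannot be checked.

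*Few events are affected.* This stands. The MAAE definition is wide, since it takes in visits to medical personnel for any reason. Allocation is by onset date. After Day 57 no vaccination remains, and scheduled contact is one call and one visit. A non-serious, unattended AE that starts that late and ends participation should be rare.

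*The comparison hardly changes.* This also largely stands. After Day 29 all groups are planned to have received both vaccines, safety is descriptive, and the primary analysis is triggered 28 days after vaccination 2.

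A reader might infer that the endpoint as a whole is tabulated for only about a quarter of follow-up, or that 73% of withdrawal AEs are lost. The documents support neither. SAEs, MAAEs and AESIs that lead to withdrawal are tabulated throughout, and 73% is a share of calendar days.

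**Conclusion.** The mismatch is real and narrow. The SAP's table rule omits a secondary endpoint that both documents define for the whole study, and nothing visible clearly restores it. Read literally, the rule under-counts the endpoint by any withdrawal AE with onset in the 152 of 208 nominal days outside the windows that is not an SAE, MAAE or AESI. It also leaves the endpoint without a specified whole-study table. The number of such events is unknown and probably small, and the effect falls mainly on the final analysis. No primary conclusion depends on it.

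This rests on three assumptions: the nominal visit schedule, 5.6.1.1 governing the tabulation of MAAEs, and the Data Presentation Specification not already giving the discontinuation row a whole-study period. It is worth correcting because a stated rule conflicts with a named endpoint and the repair is cheap. It should not be read as evidence that the by-group count will be wrong: the count differs only if such an event occurs and the rule is applied literally.

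**What to change.** Change the SAP only:

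- In 5.6.1.1, add AEs leading to withdrawal from the study to the categories tabulated over the whole study.
- In 5.6.1.2, state that the discontinuation row of the unsolicited AE summary table covers the whole study.
- In 5.6.1.2, exempt these events from the rule that sends late non-serious AEs to listings.

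The cost is a few words of SAP text and a matching output specification. The data are already collected, and no hypothesis, sample size or study procedure changes. Protocol 9.4.5 has the same omission, but Protocol 10.3.1 requires a formal amendment for any modification, and this point does not justify one by itself. Align 9.4.5 at the next amendment.
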